5.5.5.1. Duration of Exposure

From the dose information recorded on the eCRF, the following duration of exposures will be derived and summarized:

- duration of exposure in days during SP III calculated as Treatment end date (disposition date in SP III) – First date IP administered during SPIII + 1

- duration of exposure in days during SP IV calculated as Treatment end date (disposition date in SP IV) – First date IP administered during SP IV + 1
- duration of exposure in days during SPIII/SP IV for the GMB-treated population calculated as GMB treatment end date (last disposition date in SP III/IV) – First date GMB administered during SP III/IV + 1

Comparisons between treatment groups will be performed for SP III using an ANOVA with treatment and pooled investigative site in the model.

The number of full doses will also be summarized.

5.5.5.2. Treatment Compliance

Treatment compliance will be calculated for SP III and SP IV separately as follows

$$\text{(number of full doses received)/(number of intended full doses)} * 100.$$

Note, full dose means that patients have to receive all 3 injections at the injection day. For patients that are early discontinued, number of intended full doses will only include scheduled doses prior to discontinuation. For SP III, comparisons between treatment groups in the ITT population for treatment compliance will be performed using an ANOVA with treatment and pooled investigative site in the model. For SP IV, treatment compliance will be summarized in the open-label population.

5.5.6. Electronic Patient-Reported Outcome Diary Compliance

Electronic patient-reported outcome diary compliance at each biweekly interval (including baseline, Weeks 1/2, 3/4, 5/6, 7/8, 9/10, 11/12, 13/14, and 15/16) and for SP III (Weeks 1/2 through 11/12) will be calculated. Diary compliance at each interval is calculated as:

$$\frac{\text{Actual number of diary entry days in the interval} * 100}{\text{Expected number of diary entry days in the interval}}$$

The diary entry can only be saved and submitted after all the required ePRO questions are answered, so the actual number of diary entry days represents the total number of days with non-missing answer to all the required cluster headache attack ePRO questions. The expected number of diary entry days will be calculated as the (last calendar date - the first calendar date in each interval+1).

Comparisons between diary compliance for each interval separately will be performed using an ANOVA with treatment and pooled investigative site in the model.

Compliance will also be listed by weekly interval for each patient.

5.5.7. Concomitant Therapy

Concomitant medications collected from eCRF or ePRO diary will be coded to PT using the World Health Organization drug dictionary. The proportion of patients who received concomitant medication (including preventive medication) collected from eCRF will be

summarized by PT separately for all ITT patients for SP III, SP IV, and SP V. If there are different PTs for salt forms of a preventive or abortive medication, these PTs will be combined for the medication in the summary. Concomitant therapies for SP III are those which stopped during SP III or continued in SP III. If medication started and stopped on the same day of first injection, it will still be considered as concomitant medication for SP III. If a medication started before the first day of injection but stopped on the same day of injection, then it will not be counted as concomitant medication for SP III. Concomitant therapies for SP IV are those which either started, stopped or continued in SP IV. Similarly, concomitant therapies for SP V are those which either started, stopped or continued in SP V.

Abortive medications for cluster headache attack collected through ePRO diary will be summarized separately by PT for all ITT patients for SP III and first month of SP IV.

Treatment group comparisons will be done using Fisher's exact test for SP III with ITT population. Descriptive statistics only will be presented for the treatment groups in SP IV and SP V.

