(Visits 4 and 7) with the patient approximately 1 week after the first two IP administration visits during SP III to collect spontaneously reported AEs. At Visit 5, the patient will come into the office for the collection of blood samples 2 weeks after the first dose. During SP III, the patient will continue to record his or her cluster headache attack information daily in the ePRO diary.

- For patients who discontinue early in SP III, they should enter SP V.
- For patients who complete SP III, SP IV is an optional 1-year exposure, open-label treatment phase which is described below.
- For patients who choose not to enter SP IV, they should enter SP V.

During SP IV, the unblinded site personnel will continue to prepare the IP for each patient. All patients who enter SP IV will receive open-label monthly injections of LY2951742. All study procedures at Visit 9 must be completed prior to patients receiving the first dose of LY2951742 in SP IV. Patients and investigators will remain blinded to the SP III treatment assignments during SP IV. Each dose of IP will be administered as 3 SC injections at office visits: Visits 9 and 11 through 21. Since placebo patients will be transitioning to LY2951742 at Visit 9, all patients should remain in the office for 30 minutes for observation after administration of IP. Also, during SP IV, some patients may transition to LY2951742 300 mg supplied in 3 prefilled syringes with each syringe containing 100 mg. These patients should remain in the office for 30 minutes for observation after the first prefilled syringe injection. All patients will continue to record his or her cluster headache attack information daily in the ePRO diary until Visit 11.

Study Phase V is a 16-week post-treatment phase for safety follow-up.

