12.2.4. Concomitant Therapy

The proportion of patients who received concomitant medication (including preventive medication) and abortive medications for cluster headache attacks will be summarized separately

for all ITT patients for SP III, SP IV and SP V. Treatment group comparisons will be done using Fisher's exact test for SP III with ITT population. Descriptive statistics only will be presented for the treatment groups in SP IV and SP V.

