5.5.1. General Considerations

General aspects of statistical analyses are described below.

Unless otherwise specified, efficacy analyses will be conducted on an **intent-to-treat (ITT) population**, which include all patients who are randomized and receive at least one dose of study drug. Patients in the ITT population will be analyzed according to the treatment group that they were randomized to. Safety analyses for SP III will be conducted on the **safety population** which also includes all patients who are randomized and receive at least one dose of study drug. However, patients will be analyzed by actual study treatment received most often (modal treatment) during the double-blind treatment phase. Modal treatment will be the same as randomized treatment except in some cases of incorrect treatment administration. When mean change from baseline is assessed, the patient will be included in the analysis only if he/she has a baseline and a post-baseline measurement.

The additional analyses populations are described in [Table CGAM.5.2](#).

Safety analyses (Section [5.5.9](#)) and analyses for exposure will be conducted based on the modal treatment group patients have received (placebo or GMB300mg) during the double-blind treatment phase. For determining modal treatment, if there are 2 modes, then the modal treatment group will be GMB300mg.

Table CGAM.5.2. Study Phase, Analysis Population and Corresponding Treatment Groups

Study Phase (SP)	Analysis Population	Population Definition	Treatment Groups
SP III	ITT Population	All patients who are randomized and receive at least one dose of study drug	SP III treatment (based on randomization): Placebo, Galcanezumab 300mg (GMB300mg)
SP III and first 4 weeks of SP IV combined ^a			
SP III	Safety Population	All patients who are randomized and receive at least one dose of study drug	SP III treatment (based on modal treatment arm): Placebo, GMB300mg
SP IV	Open-label population	All patients who entered the open-label extension phase (SP IV) as indicated by receiving any injections in any open-label extension visit	SP III/IV treatment: Placebo-GMB300mg, GMB300mg-GMB300mg
SP III/IV Combined (GMB-treated time)	GMB-treated population	All patients who have exposure to Galcanezumab: 1) patients who received GMB300mg during SP III;	SP III/IV treatment: GMB300mg

Study Phase (SP)	Analysis Population	Population Definition	Treatment Groups

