5.5.2. Patient Disposition

The number and percentage of ITT patients who complete the study or discontinue early will be tabulated for all treatment groups for SP III, SP IV, and SP V, both overall and by visit. Reasons for discontinuation will be compared between treatment groups using Fisher's exact test for SP III with the ITT population. Descriptive statistics only will be presented for the treatment groups in SP IV and SP V. For patients who were randomized without drug injection, reasons for early discontinuation will be provided in a listing.

Patient allocation by investigator will be summarized for SP III for all ITT patients.

Patient allocation by investigator will also be listed for all study phases.

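### SP IV concomitant-medication percentages are specified for all ITT patients, so patients who never entered that optional phase count as non-users

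*SAP*

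**What the plan says.** SAP 5.5.7 has the proportion of patients with eCRF-recorded concomitant medication "summarized by PT separately for all ITT patients for SP III, SP IV, and SP V". Protocol 12.2.4 has it "for all ITT patients for SP III, SP IV and SP V". The ITT population is "all patients who are randomized and receive at least one dose of study drug" (SAP 5.5.1), so entry to SP IV is not required for membership.

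Protocol 7.1 makes SP IV conditional and voluntary: "For patients who complete SP III, SP IV is an optional 1-year exposure, open-label treatment phase". SAP 5.5.7 assigns a therapy to SP IV only if it began, ended or was ongoing in that phase.

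The SAP has a population built for SP IV. Table CGAM.5.2 in 5.5.1 defines the open-label population as "All patients who entered the open-label extension phase (SP IV) as indicated by receiving any injections in any open-label extension visit" and pairs it with two groups, placebo then galcanezumab and galcanezumab throughout. Section 5.5.5.2 applies it: "For SP IV, treatment compliance will be summarized in the open-label population". That section keeps ITT for the SP III compliance comparison.

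Two neighbouring rules also name ITT. Abortive medication from the diary is summarized "for all ITT patients for SP III and first month of SP IV" (SAP 5.5.7). For disposition, "The number and percentage of ITT patients who complete the study or discontinue early will be tabulated for all treatment groups" for each of SP III, SP IV and SP V (SAP 5.5.2).

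**The concern.** A table of concomitant medication in the open-label year would normally be read as the share of open-label patients who took each drug. With ITT as the denominator it reports the product of two things: how many patients entered the phase, and how many of those used the drug. The first depends on SP III dropout and on willingness to continue, and neither is medication use.

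Two consequences follow. Every SP IV percentage falls below use among entrants by the factor of the entry rate. A difference between the two sequences can also arise from unequal entry alone. In addition, the SAP would describe one phase on two bases, compliance on entrants and concomitant medication on ITT, without giving a reason.

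**Working it through.** The documents give no percentage or denominator count for these tables, so there is no stated figure to reproduce. The check is on the rule itself.

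**Inputs**
- Planned randomized: 162. Planned SP III completers: 146 (protocol synopsis).
- Entry to SP IV: SP III completers only, and voluntary (protocol 7.1).
- Use rates, and all entry rates other than 146/162, are assumptions. The documents give none.

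**Step 1: who can be counted.** A therapy counts for SP IV only if it falls in SP IV, so only entrants can be in the numerator. The named population also includes non-entrants.

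**Step 2: formula.** Let N be the ITT patients, E the SP IV entrants and U the entrants using a drug. The percentage on ITT is U/N = (U/E) × (E/N), that is, use among entrants times the entry rate. The percentage on the open-label population is U/E.

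**Step 3: entry rate on the planned figures.** If every planned completer enters, E/N = 146/162 = 0.901. This takes all 162 randomized patients as ITT.

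**Step 4: effect on a single percentage**
- True 60%, all completers enter: 0.60 × 146/162 = 54.1%.
- True 60%, 75% of completers enter (assumption): 0.60 × (0.75 × 146)/162 = 40.6%.
- True 30% and true 80%, all completers enter: 27.0% and 72.1%.

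**Step 5: effect on the comparison of sequences**
- Equal use of 60%, entry of 95% and 80% (assumptions): 0.60 × 0.95 = 57% and 0.60 × 0.80 = 48%. The 9-point gap comes from entry alone.
- Equal use of 50%, entry of 90% and 80% (assumptions): 45.0% and 40.0%, a gap of 5 points.
- Unequal use can hide the effect. Use of 50% at 90% entry and use of 60% at 75% entry both read 45.0%.

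**Step 6: SP V.** The same formula applies, but the routing differs. Protocol 7.1 sends both early SP III discontinuations and patients who decline SP IV to SP V. If all ITT patients enter SP V, a true 50% reads 50%. At 85% entry (assumption) it reads 42.5%.

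**The case against.** The strongest reply is that the denominator is inferred. Section 5.5.7 names the patients to be summarized and then refers to the treatment groups in SP IV, and Table CGAM.5.2 attaches those groups to the open-label population. The phrase could therefore mean ITT patients who were in the phase. That reading is possible, but it goes against the plain words, and it leaves two programmers free to produce different tables. The rule needs correcting on either reading.

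Other parts of the reply stand in full and limit the point:

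- A reader might infer that the first-month abortive summary contradicts the SAP. It does not. Table CGAM.5.2 assigns ITT to SP III plus the first four weeks of SP IV, and its footnote reserves that row for diary data, which is how abortive use is collected.
- A reader might carry the argument from SP IV's optional status over to SP V. It does not carry, because decliners and early discontinuations are routed there. What remains is that SAP 5.5.1.5 lists no SP V population, that some patients may refuse follow-up (protocol 8.4.2 allows for this), and that some will not have reached SP V at interim analysis 2. The last effect is temporary, because SAP 5.8.1.2 reruns SP IV and SP V analyses at final lock.
- A reader might call ITT-based disposition wrong. The share of treated patients who complete each phase is a legitimate retention measure.
- A reader might treat 90.1% as a hard ceiling, or expect sequences to differ whenever entry rates differ. The 146 is a planned count, 162 is a minimum that may be increased, and Step 5 shows that effects can offset.

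**Conclusion.** The point holds for eCRF concomitant medication in SP IV. Followed as written, SAP 5.5.7 and protocol 12.2.4 multiply use among entrants by the entry rate, and they depart from the SAP's own population for that phase. If planned completion is realised and every completer enters, the reduction is about 10% in relative terms, and it is larger if some decline. An artificial gap between sequences requires unequal entry. Its size depends on entry and use rates that the documents do not give, so the 5- and 9-point figures are illustrations only.

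The importance is low. SP IV and SP V concomitant-therapy tables are descriptive and carry no test. The finding is a wrong denominator in supportive tables; it does not threaten the trial's conclusions.

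**What to change.** In SAP 5.5.7, with matching wording in protocol 12.2.4:

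- **SP III:** keep the ITT population.
- **SP IV eCRF medication:** use the open-label population, by SP III/IV sequence, as the denominator.
- **SP V medication:** use patients who entered SP V, and define that set in SAP 5.5.1.
- **First-month abortive medication:** leave it on the ITT/ePRO row of Table CGAM.5.2, and show the number of SP IV entrants beside it.

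In SAP 5.5.2, keep disposition on ITT and add a row for the number entering each phase, so that a reader can obtain either percentage.

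The cost is a few lines of text and revised table shells. No new data or analysis method is needed. The one disadvantage is smaller denominators in the SP IV and SP V tables.

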5.5.8. Efficacy Analyses

5.5.8.1. Primary Outcome and Methodology

The primary analysis will be conducted by a restricted maximum likelihood-based (REML-based), mixed-effects repeated measures (MMRM) analysis using all the longitudinal observations at Weeks 1/2, 3/4, 5/6, 7/8, 9/10, and 11/12. The analysis of the primary outcome will be the main effect of treatment between galcanezumab 300 mg and placebo during the 12-week double-blind treatment phase from a repeated measures analysis on mean change from baseline in the weekly cluster headache attack frequency. This provides the average treatment effect across the 12-week double-blind treatment phase. Baseline is defined as the last 14 days in the eligibility report (pre-randomization diary phase). In addition to the primary endpoint results, the LSMeans, standard errors, along with 95% CIs for the mean change from baseline for GMB300mg and placebo at each bi-weekly interval will also be reported from the MMRM.

The model for the primary analysis will include the fixed, categorical effects of treatment, gender, verapamil use, pooled investigative site, week, and treatment-by-week interaction, as well as the continuous, fixed covariates of baseline value. An unstructured covariance structure will be used to model the within-patient errors. The Kenward-Roger (Kenward and Roger 1997) approximation will be used to estimate denominator degrees of freedom. If the model does not converge with both the Hessian and the G matrix being positive definite under the default fitting algorithm used by PROC MIXED, the Fisher's scoring algorithm will be implemented by specifying the SCORING option in SAS®. If the model still fails to converge, the model will be fit using covariance matrices of the following order specified by a decreasing number of covariance parameters until convergence is met:

- heterogeneous Toeplitz
- heterogeneous first-order autoregressive

- Toeplitz
- first-order autoregressive

If necessary, both the default and the scoring fitting algorithms will be used in the pre-specified order before proceeding to the next covariance structure in the sequence. For models where the unstructured covariance matrix is not utilized, the sandwich estimator (Diggle et al. 1994) will be used to estimate the standard errors of the fixed effects parameters. The sandwich estimator is implemented by specifying the EMPIRICAL option in SAS®. When the sandwich estimator is utilized, the Kenward-Roger approximation for denominator degrees of freedom cannot be used. Instead, the denominator degrees of freedom will be partitioned into between-subject and within-subject portions by the DDFM=BETWITHIN option in SAS®. SAS® PROC MIXED will be used to perform the analysis.

If the sample size is not increased, a conventional analysis based on the single contrast with MMRM as specified above will be conducted. If the sample size is increased as a result of the interim analysis, the Cui, Hung, and Wang (CHW) procedure (Cui et al. 1999) will be applied to the primary endpoint to control the Type I error at a one sided $\alpha=0.025$ significance level. The CHW method ensures strong control of Type I error when the sample size is increased in a data dependent manner. The detailed approach to control Type I error using CHW procedure is described in [Appendix 1](#).

If the sample size is increased as a result of the interim analysis, an unadjusted point estimate for the primary efficacy analysis will be calculated and reported. A median unbiased point estimate and a stage-wise adjusted confidence interval for the primary efficacy analysis will be calculated and reported based on the approach described in Brannath et al. 2009 to assess sensitivity of the point estimate.

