The aim of this study is to assess the safety and efficacy of LY2951742 300 mg administered every 30 days for the prevention of chronic cluster headache.

Clinical Protocol Synopsis: Study I5Q-MC-CGAM

Name of Investigational Product: LY2951742	
Title of Study: A Phase 3 Randomized, Double-Blind, Placebo-Controlled Study of LY2951742 with a Long-Term Open-Label Extension in Patients with Chronic Cluster Headache	
Number of Planned Patients/Subjects: Entered: 231 Enrolled/Randomized: Planned 162 Completed (SP III): 146	Phase of Development: 3
Length of Study: 30 months	
Estimated first patient visit: Jun 2015 Estimated last patient visit: Dec 2017	
Primary Objectives: The primary objective is to assess the efficacy of LY2951742 300 mg administered every 30 days compared with placebo in reducing the frequency of weekly cluster headache attacks in patients with chronic cluster headache. The primary outcome measure is the weekly cluster headache attack frequency. The primary endpoint is the overall mean change from baseline in weekly cluster headache attack frequency during the 12-week double-blind treatment phase with LY2951742 compared with placebo. The baseline cluster headache attack frequency is based on the last 14 days in the eligibility report (pre-randomization diary phase).	
Gated Objectives: 
• To assess the efficacy of LY2951742 300 mg compared with placebo in the estimated mean proportion of patients with a 50% or greater reduction from baseline in the weekly frequency of cluster headache attacks during the 12-week double-blind treatment phase.• To assess the efficacy of LY2951742 300 mg compared with placebo in the proportion of patients meeting sustained response through Week 12. For this analysis, sustained response is defined as a 50% or greater reduction in the weekly cluster headache attack frequency from baseline to Weeks 3/4 and maintained at Weeks 5/6, Weeks 7/8, Weeks 9/10, and Weeks 11/12.	

Other secondary objectives:

- To assess whether LY2951742 300 mg is superior to placebo on the following:
 - mean change in the weekly cluster headache attack frequency from baseline to each 2-week interval through Week 12
 - the proportion of patients with a 50% or greater reduction in the weekly cluster headache attack frequency from baseline at each 2-week interval through Week 12

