5.2. Determination of Sample Size

The study is planned to have a minimum of approximately 162 patients randomized 1:1 to placebo or galcanezumab 300 mg with the opportunity to increase the final sample size at an interim analysis if indicated in order to maintain a well powered study. To preserve blinding, details of the sample size and power calculations are omitted from this SAP and are provided in a separate document to the Ethical Review Board (ERB).

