5.5.1.4. Multiple Comparisons/Multiplicity

The primary efficacy analysis will be the overall treatment effect of galcanezumab 300 mg every 30 days vs. placebo using a MMRM analysis, which is equivalent to the average of the MMRM-estimated weekly treatment effect over the 12-week double-blind treatment phase for change in weekly cluster headache attack frequency from baseline. The Type I error rate will be controlled at a 1-sided 0.025 level for the primary efficacy analysis.

A fixed sequential gatekeeper method will be utilized for testing secondary hypotheses to be eligible for inclusion in the proposed label. Specific details of the testing of the secondary gatekeeper objectives are provided in Section [5.5.8.2](#).

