5.5.8.2. Gated Secondary

For the gated secondary of the estimated mean proportion of patients with a 50% or greater reduction from baseline in the weekly frequency of cluster headache attacks during the 12-week double-blind treatment phase, a categorical, pseudo-likelihood-based repeated measures analysis will be used. The endpoint for comparing GMB300mg with placebo will be estimated as the main effect of treatment from the categorical MMRM analysis across Weeks 1-12. This analysis will be implemented using the GLIMMIX procedure in SAS® to compare treatments and include the fixed, categorical effects of treatment, gender, verapamil use, visit/week, and treatment-by-visit/week interaction, as well as the continuous, fixed covariate of baseline value. An unstructured covariance structure will be used to model the within-patient errors (denoted by TYPE=CHOL in the RANDOM statement). The Newton-Raphson method with ridging will be used for nonlinear optimization (denoted by including NLOPTIONS TECH=NRRIDG). The Kenward-Roger approximation will be used to estimate denominator degrees of freedom. If the model does not converge, the Fisher's scoring algorithm will be utilized by the SCORING option in SAS®. If the model still fails to converge, the model will be fit using covariance matrices in the following order specified by a decreasing number of covariance parameters until convergence is met: heterogeneous Toeplitz, heterogeneous autoregressive, Toeplitz, and

autoregressive. If necessary, both fitting algorithms will be used in the pre-specified order before proceeding to the next covariance structure in the sequence. For models where the unstructured covariance matrix is not utilized, the sandwich estimator (Diggle et al. 1994) will be used to estimate the standard errors of the fixed effects parameters. The sandwich estimator is utilized by the EMPIRICAL option in SAS®. When the sandwich estimator is utilized, the Kenward-Roger approximation for denominator degrees of freedom cannot be used. Instead, the denominator degrees of freedom will be partitioned into between-subject and within-subject portions by the DDFM=BETWITHIN option in SAS®.

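### If the unstructured covariance fails to converge, the primary MMRM falls back to an uncorrected sandwich standard error with pooled site still in the model, and that fallback test runs above its one-sided 0.025 level

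*SAP*

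**What the plan says.** SAP 5.5.8.1 fits a REML repeated-measures model "using all the longitudinal observations at Weeks 1/2, 3/4, 5/6, 7/8, 9/10, and 11/12". Its fixed effects are treatment, gender, verapamil use, pooled site, week, treatment-by-week and baseline. The first choice is an unstructured covariance with Kenward-Roger degrees of freedom.

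If this fails under both the default and the scoring algorithm, the plan moves in turn to heterogeneous Toeplitz, heterogeneous first-order autoregressive, Toeplitz and first-order autoregressive. On each of these steps the standard errors come from the sandwich: "The sandwich estimator is implemented by specifying the EMPIRICAL option in SAS". The section adds: "When the sandwich estimator is utilized, the Kenward-Roger approximation for denominator degrees of freedom cannot be used". Between-within degrees of freedom replace it. Protocol 12.2.7.1 gives the same fallback. Neither document names a small-sample correction to the sandwich, and neither removes pooled site on this path.

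SAP 5.5.1.4 states the target: "The Type I error rate will be controlled at a 1-sided 0.025 level for the primary efficacy analysis". If the sample size is increased, Appendix 1 takes the two CHW components from separate fits to the interim and post-interim patients.

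**The concern.** The uncorrected sandwich builds the variance from squared residuals. Fitting many between-patient parameters shrinks those residuals, so the standard error of the treatment effect comes out too small. Each pooled site adds one such parameter. Kenward-Roger is the plan's small-sample protection, and it is dropped on this path with nothing equivalent put in its place.

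At stake is the primary p-value and its confidence interval. Once the fallback is triggered it is the primary analysis, and it should hold the level that 5.5.1.4 promises. CHW combination preserves the type I error only if each stage's statistic is valid, so an error in the stage-wise standard errors passes straight through.

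**Working it through.** **Inputs from the documents**
- N: "minimum of approximately 162 patients randomized 1:1 to placebo or galcanezumab 300 mg" (SAP 5.2).
- Dropout: "Enrolled/Randomized: Planned 162 Completed (SP III): 146" (Protocol synopsis), so (162 − 146)/162 = 9.9%.
- Six intervals, so the unstructured matrix has 6 × 7/2 = 21 parameters.
- CHW quantities (Appendix 1): n1 = 114 (70% of 162 = 113.4) and n2 = 48 (162 − 114).
- Minimization with probability 0.8 (SAP 5.3).
- Effect size and SD are withheld; they are not needed for an error rate under the null.

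**Assumed input: the number of pooled sites, S.** The pooling rule in SAP 5.5.1.3 aims at 2 or more patients per arm, so at least 4 per pooled site. That allows S up to 40 at 162 patients (162/4 = 40.5) and up to 28 at 114 (114/4 = 28.5).

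**Step 1. The plan's own figure on the first-choice path.** A null simulation used six intervals, minimization and 9.9% monotone dropout, with 8,000 trials per S and a Monte Carlo SE of about 0.0012. The unstructured model-based test, with t degrees of freedom standing in for Kenward-Roger, gave a one-sided level of 0.0236 to 0.0271 for S from 1 to 40. The stated 0.025 is reproduced.

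**Step 2. The fallback by formula.** The between-patient parameters number p = S + 4 (sites including the intercept, treatment, gender, verapamil, baseline). The uncorrected sandwich keeps about 1 − p/N of the true variance, so

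level ≈ 1 − Φ( t(0.975, N − p) × √(1 − p/N) ).

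For example, with N = 162 and S = 20: p = 24, df = 138, t = 1.977, 1 − 24/162 = 0.852, √0.852 = 0.923, 1.977 × 0.923 = 1.825, level = 0.0340. The lower df moves the cut-off only from 1.960 to 1.977, while the standard error falls by 7.7%.

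| N | S | p | df | 1 − p/N | Level, formula | Level, six-interval simulation |
|---|---|---|---|---|---|---|
| 162 | 1 | 5 | 157 | 0.969 | 0.0259 | 0.0286 |
| 162 | 5 | 9 | 153 | 0.944 | 0.0274 | 0.0274 |
| 162 | 10 | 14 | 148 | 0.914 | 0.0295 | 0.0317 |
| 162 | 20 | 24 | 138 | 0.852 | 0.0340 | 0.0331 |
| 162 | 30 | 34 | 128 | 0.790 | 0.0393 | 0.0385 |
| 162 | 40 | 44 | 118 | 0.728 | 0.0455 | 0.0457 |
| 114 | 10 | 14 | 100 | 0.877 | 0.0316 | not run |
| 114 | 20 | 24 | 90 | 0.789 | 0.0388 | not run |
| 114 | 28 | 32 | 82 | 0.719 | 0.0458 | not run |

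The simulated fallback used heterogeneous Toeplitz with the uncorrected sandwich and between-within df.

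**Step 3. A separate patient-level null simulation** regressed each patient's 12-week mean change on the same between-patient terms. It gave 0.028, 0.033 and 0.043 at N = 162 with S = 10, 20 and 30, and 0.035 to 0.046 at N = 114 with S = 10 to 28. The formula puts the lower end at N = 114 slightly lower, at 0.032.

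**Step 4. CHW, illustrative.** Assume 100 post-interim patients and the fallback in both stages. The combined variance relative to nominal is (114/162)/(1 − p/114) + (48/162)/(1 − p/100). For S = 20 this is 0.704/0.789 + 0.296/0.76 = 1.281, and 1 − Φ(1.96/√1.281) = 0.042. Simulation (3,000 trials, SE about 0.002) gave 0.031, 0.042 and 0.050 at S = 10, 20 and 28. Model-based fits in the same runs gave 0.025, 0.028 and 0.030, so part of the excess at larger S comes from using t statistics as z.

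**Step 5. Corrections.** A leverage correction to the same sandwich, with the same df, gave 0.0274, 0.0238, 0.0264, 0.0244, 0.0261 and 0.0260 for S = 1, 5, 10, 20, 30 and 40 in the six-interval simulation. In the patient-level check, the square-root-leverage form and the model-based test both stayed at 0.022 to 0.027. A full inverse-leverage (Mancl-DeRouen-type) correction over-corrects. It gave 0.0171 at S = 20 and 0.0125 at S = 40 in the six-interval run. In the patient-level run it gave 0.016 at N = 162 with S = 20 and 0.010 at N = 114 with S = 28.

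**The case against.** **The fallback may never be used.** It needs 21 covariance parameters to fail under two algorithms with about 10% dropout. Unstructured REML fitted to simulated heavy-tailed data with that dropout converged in 200 of 200 trials, at 60 to 162 patients. That run used a different optimiser from SAS and an assumed data model, so it does not settle the probability, but nothing suggests a common trigger. This stands: the unconditional excess is the probability of fallback times roughly 0.01, and may be negligible. It does not excuse a prespecified primary test that misses its level when it is used.

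**A check is already planned.** SAP 5.5.11 has a 100,000-draw permutation test that uses the exact minimization and pooling algorithms, and Appendix 1 extends it to CHW. It should expose the discrepancy. But it is a sensitivity analysis and does not replace the primary p-value.

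**The site count is unknown.** This also stands. With 1 to 5 pooled sites the excess is negligible to small (0.026 to 0.029).

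**Two stronger readings are not supported.** A reader might infer a still worse level in a 48-patient second stage. No such fit is planned: CHW applies only after an increase, 48 only fixes the weights, and the second stage would then exceed 48. A reader might also carry the point to the gated 50% response analysis, because SAP 5.5.8.2 has the same wording ("The sandwich estimator is utilized by the EMPIRICAL option in SAS"). That model has no site terms; SAP 5.5.1.1 leaves them out to help convergence. The mechanism is therefore largely absent there, and no binary model was simulated.

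**Conclusion.** The point holds, conditional on the fallback and for the primary analysis only. Given fallback, the one-sided level is about 0.028 to 0.043 at 162 patients with 10 to 30 pooled sites and about 0.035 to 0.046 at 114 patients with 10 to 28, against a stated 0.025. CHW statistics inherit the error if the sample size is increased and a stage fit falls back.

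This rests on an assumed number of pooled sites, on normal data in the simulations, and on reading the EMPIRICAL option as the classical uncorrected sandwich, since the documents name no correction.

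A reader might infer that the trial's primary test exceeds 0.025 outright, or that the smaller stage-wise fits are likely to fail. The documents support neither: the unstructured path holds its level, and they give no basis for a probability of non-convergence. This is a defect in a contingency rule that is cheap to repair.

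**What to change.** In SAP 5.5.8.1 and Protocol 12.2.7.1, state that when the unstructured matrix is not used, the standard errors come from a sandwich with a square-root-leverage small-sample correction (Kauermann-Carroll or HC2-type). Keep the order of covariance structures and the between-within degrees of freedom. Do not name a full inverse-leverage correction, which is conservative here and would lose power. Apply the same rule to both stage-wise fits in Appendix 1. SAP 5.5.8.2 need not change on this ground.

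The cost is a sentence in each document and a change of programming option, made before the study team is unblinded at the second interim analysis. Intervals become slightly wider, on the fallback path only.
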